6.3. Safety Assessments

6.3.1. Adverse Events

All AEs will be collected from the time the subject signs the ICF until the final visit/contact with the subject. Additional safety information, including the definition of an AE and the methods for recording, evaluating, and assessing causality of AEs and the procedures for completing and transmitting SAE reports are provided in [Section 8](#).

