7.4. Follow-Up Visit 7; Week 16 (Day 113 ±4 Days)

Subjects who do not enroll in the open-label long-term study will return to the study site at Week 16 to complete follow-up assessments as follows:

- Urine pregnancy test (females of child-bearing potential)
- Brief physical examination
- Vital signs measurement
- Blood sample collection for clinical laboratory tests
- Urinalysis
- PGA score
- %BSA affected calculation (performed before PASI)
- PASI
- LTS
- DLQI
- SF-36
- PSD
- Peak Pruritus-NRS
- AE recording
- Concomitant medication recording

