## 9. HANDLING OF MISSING DATA

### Imputation of Start and End Dates of Adverse Event (AE)

To calculate duration of Adverse Events, the following rules will be used where applicable to impute partial or completely missing start dates or end dates:

- If only the day is missing for a start date, the 1st of the month will be imputed. If the new estimated date falls before the date of first dose, while the known month and year match the month and year of the first dose, the date of first dose will be used as the new estimated date. The AE will be considered as a treatment-emergent AE (TEAE).
- If only the day is missing for an end date, the last day of the month will be imputed. If the new estimated date falls after the date of last study visit, the date of last study visit will be used as the new estimated date. Last study visit is defined as the Week 12 visit for those who elect to participate in the open-label long-term study, or the Week 16 Follow-up visit for those who fail to qualify for participation in the open-label study, or who qualify to participate but ultimately elect not to enroll.
- If both the day and the month are missing for a start date or end date, no imputation will be used, and the duration will not be calculated. However, if the year of start is the same or greater than the year of the first dose date, the AE will be considered as treatment emergent.

- If the start date or end date is completely missing, duration will not be calculated. However, an event with completely missing start date will be considered as treatment emergent.

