### **12.9.1 Adverse Events**

AE terms will be coded using the MedDRA dictionary. A treatment-emergent AE (TEAE) is defined as an AE that starts after the first dose of study medication. For subjects not rolling over to Open-label study, all reported AEs will be included in the Double-Blind phase summaries. For subjects rolling over to the Open-label study, all AEs with an onset date on or before the Week 12 visit date will be included in the Double-Blind phase summaries.

If relationship to treatment is missing, the event will be conservatively treated as related to study drug. Missing severity will be imputed to the highest severity level (most severe).

All AEs will be listed by treatment and by subject, detailing the verbatim term given by the investigator, the preferred term (PT), system organ class (SOC), onset date and time, end date and time, duration (days), CTCAE grade, outcome, relationship to study drug/treatment, action taken with study drug/treatment, other action taken to treat the event, seriousness and criteria for seriousness. Serious AEs (SAEs), TEAEs leading to study discontinuation, TEAEs related to study drug will also be listed separately. The following adverse event of special interest (AESIs) will be identified and listed separately: contact dermatitis, folliculitis, and headache.

AEs will be summarized by treatment and overall as incidence rates of:

- Any AE
- Any TEAE
- Any AESIs
- Any treatment-related TEAE, including definitely, probably, and possibly related
- Any TEAE leading to study drug discontinuation
- Any SAE (non-Fatal)
- Any serious TEAE
- Death
- Treatment-related Serious TEAE
- Serious TEAE leading to study drug discontinuation

Individual PTs will be summarized by treatment according to the following:

- All TEAEs by SOC in alphabetical order and PT in descending order of combined frequency (also for treatment-related TEAEs, TEAEs leading to study discontinuation and serious TEAEs)
- All TEAEs by SOC, PT, and maximum CTCAE grade
- All TEAEs by SOC, PT, and maximum causality (not related, related) to the study drug

In addition, TEAEs and serious TEAEs will be summarized by SOC (alphabetical order) and PT (descending order) for the following subgroups:

- Age (<65 and >= 65 years old)
- Sex
- Race (White, Other)

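### The double-blind AE tables count events to Week 16 for completers who decline the open-label study and to Week 12 for those who enter it, so crude AE percentages depend on roll-over

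*SAP*

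**What the plan says.** SAP 12.9.1 sets the window by roll-over status. For one group, "For subjects not rolling over to Open-label study, all reported AEs will be included in the Double-Blind phase summaries". For subjects who roll over, "all AEs with an onset date on or before the Week 12 visit date will be included in the Double-Blind phase summaries". SAP Section 9 makes the same split when it imputes AE dates: "Last study visit is defined as the Week 12 visit for those who elect to participate in the open-label long-term study", and the Week 16 visit for the others.

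The protocol supplies the extra observation time. Section 6.3.1 states: "All AEs will be collected from the time the subject signs the ICF until the final visit/contact with the subject". Section 7.4 states: "Subjects who do not enroll in the open-label long-term study will return to the study site at Week 16 to complete follow-up assessments", and AE recording is on the list for that visit.

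The TEAE definition has a start but no end: "A treatment-emergent AE (TEAE) is defined as an AE that starts after the first dose of study medication". The tables are introduced with "AEs will be summarized by treatment and overall as incidence rates of", but no person-time denominator is given and each subject counts once at each level. These are therefore crude percentages. No exposure-adjusted or common-window AE table is planned. The only AE analysis that allows for unequal follow-up is the Kaplan-Meier figure of time to first event for each AESI (contact dermatitis, folliculitis, headache), also in 12.9.1.

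**The concern.** Crude AE percentages by arm are the main safety display of a vehicle-controlled trial. They compare like with like only if subjects in both arms are observed for similar periods. Here the period depends on whether a subject chooses, and qualifies, to enter another study. That is settled after randomization, and nothing in the design balances it between arms.

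The tables also carry the double-blind label, while Protocol 3.2 describes that phase as 12 weeks of treatment and Table 1 gives the follow-up visit its own column outside it. Off-drug events from one self-selected subset thus enter tables that read as treatment-phase results. Elsewhere the SAP keeps Week 16 apart. Efficacy imputation stops at Week 12 (Section 9), early termination and unscheduled assessments are windowed separately to Week 12 or Week 16 (11.4), and local tolerability, laboratory and vital-sign data are summarized by visit (12.9.2 to 12.9.4). The AE incidence tables pool the two periods.

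At stake is a descriptive comparison. No test or error rate is involved.

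**Working it through.** **Inputs from the documents.** Week 12 is Day 85 and Week 16 is Day 113 (Protocol Table 1; SAP 11.4). Screening lasts up to 34 days. Total study duration is about 20 weeks without roll-over and about 16 weeks with it (Protocol 3.1).

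**Assumed inputs.** The documents do not give the share f of completers who do not roll over, the 12-week AE risk p, or the hazard after treatment stops. I take f from 10% to 50%, p from 10% to 50%, and a constant hazard unless stated. The two arms have the same true risk throughout.

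**Step 1: the plan's own figure.** 113 − 85 = 28 days = 4 weeks. With screening, 34/7 + 12 + 4 = 20.9 weeks and 34/7 + 12 = 16.9 weeks. The protocol calls these about 20 and 16, and the 4-week gap is reproduced. The extra time is 28/85 = 33% of the 12-week window.

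**Step 2: a completer who does not roll over.** p16 = 1 − (1 − p)^(113/85). For p = 30%: 1 − 0.70^1.329 = 37.8%.

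**Step 3: the arm percentage among completers.** Observed = (1 − f) × p + f × p16.

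- f = 10%: 0.90 × 0.300 + 0.10 × 0.3776 = 30.8%
- f = 30%: 0.70 × 0.300 + 0.30 × 0.3776 = 32.3%

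The difference is (0.30 − 0.10) × (0.3776 − 0.300) = 0.0155, about 1.6 points, with no difference in true risk.

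**Step 4: range.** Differences are taken before rounding.

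| 12-week risk | p16 | f = 10% vs 30% | Difference | Difference at f = 10% vs 50% |
|---|---|---|---|---|
| 10% | 13.1% | 10.3% vs 10.9% | 0.6 points | 1.2 points |
| 30% | 37.8% | 30.8% vs 32.3% | 1.6 points | 3.1 points |
| 50% | 60.2% | 51.0% vs 53.1% | 2.0 points | 4.1 points |

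**Step 5: what moves the result.**

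- Off-drug hazard half the on-drug hazard: the exponent becomes 1 + 0.5 × 28/85 = 1.165, p16 = 34.0%, and the arms show 30.4% vs 31.2%, a gap of 0.8 points.
- Equal f in both arms: the difference is zero, but at f = 10% each arm still shows 30.8% where the 12-week incidence is 30%.
- The two values of f swapped between arms: the sign reverses.
- Early withdrawers: not in this formula. Their window ends at last contact, so a group made up largely of withdrawers could shrink or reverse the shift.

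**Step 6: with one common cut.** If every completer's window ends at the Week 12 visit, f drops out and both arms show 30.0% at any roll-over split.

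**The case against.** The strongest reply is that the SAP follows the protocol. The Synopsis and Section 10.4.3 run AE summaries from first dose to the final study visit, and 10.4.3 separates double-blind from open-label events. Subjects who roll over then start open-label treatment, so their double-blind window has to close at Week 12. This explains the rule, and it means a Week 12 cut is a departure to be documented. It does not make the windows comparable, because the final visit itself varies with roll-over.

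The second reply is that readers are partly protected. SAP 12.1 reports days in study and open-label enrolment by arm, the AE listings carry onset dates, each AESI has a censored Kaplan-Meier figure, and no formal safety comparisons are made. This stands in part. Readers could see unequal follow-up, but the tables for any, related and serious TEAEs, and those by SOC and PT, would give no corrected figure.

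The third reply is that the size rests on assumptions and probably leans high, since local reactions to a cream would plausibly become less frequent after it is stopped. This also stands, and Step 5 shows its effect.

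Two stronger readings are tempting. A reader might infer that roll-over follows response and tolerability, so the arms will differ in a predictable direction. The documents do not say so. Subjects may elect, decline or fail to qualify, and the entry rules sit in a separate protocol. A reader might also take every non-roll-over subject to be counted for 16 weeks. That holds only for completers. The plan assumes up to 25% lost to follow-up by Week 12, and those subjects are in the same group.

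**Conclusion.** The point holds as a minor flaw in a descriptive analysis. The main AE tables mix a 12-week window with a window about 28 days longer, according to a post-randomization event, in crude percentages. If roll-over differs by arm, arms with equal risk will show unequal percentages. The gap is about 1.6 points for 10% versus 30% non-roll-over at a 30% risk, and 0.6 to 4.1 points across the constant-hazard cases tabulated. These figures assume a constant hazard, equal true risk in both arms, and completers only. They fall by about half if the off-drug hazard is half, and to zero if roll-over is equal. Because the documents give no roll-over share for either arm, neither the size nor the direction in this trial can be stated, and the documents do not support a claim that the tables favor either arm.

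**What to change.** In SAP 12.9.1:

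- Base the main TEAE tables on onset from first dose to the Week 12 visit, or the Early Termination visit for those who withdraw, for all subjects. State what closes the window when neither visit takes place.
- Tabulate AEs with later onset, from the follow-up period, separately by arm.
- Keep the protocol-defined summary from first dose to final visit as a supplementary table.
- Record the change in SAP Section 13, which currently lists only the SF-36 change and the COVID-19 additions.

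The cost is one or two extra tables and a documented departure from the protocol's AE summary window. Data collection does not change, no event is lost, and safety remains descriptive. A common cut removes the artefact among completers. It does not correct for shorter observation of early withdrawers, for which exposure-adjusted rates could be added.

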8.2. Classification of Adverse Events

8.2.1. Assigning Severity Rating for Adverse Events

8.2.1.1. Criteria for Determining Averse Event Severity

The Investigator will make an assessment of the severity of each AE and SAE according to the National Cancer Institute Common Terminology Criteria for Adverse Events (CTCAE), v. 5.0, 2017. For terms not specified with the CTCAE, the criteria in [Table 4](#) should be used to determine the grade severity.

Table 4: Criteria for Determining the Grade/Severity of Adverse Event Terms Not Specified by the National Cancer Institute CTCAE

Grade	Criteria
1	Mild; asymptomatic or mild symptoms, clinical or diagnostic observations only; intervention not indicated
2	Moderate; minimal, local, or noninvasive intervention indicated; limiting age-appropriate instrumental activities of daily living ^a
3	Severe or medically significant but not immediately life-threatening; hospitalization or prolongation of hospitalization indicated; disabling; limiting self-care activities of daily living ^b
4	Life threatening consequences; urgent intervention indicated
5	Death related to adverse event

CTCAE = Common Terminology Criteria for Adverse Events.

^a Instrumental activities of daily living refer to preparing meals, shopping for groceries or clothes, using the telephone, managing money, etc.

^b Self-care activities of daily living refer to bathing, dressing and undressing, feeding self, using the toilet, taking medications, and not bedridden.

Adverse event severity should be recorded in the appropriate section of the adverse event case report form and in the subject’s source documents.

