At each level of summarization, a subject will be counted once if he/she reported one or more events. The severity of TEAEs and relationship to study drug will be summarized in a similar manner. For summaries of relationship to study drug, a subject will be classified according to the closest relationship. For summaries of TEAE CTCAE grade, a subject will be classified according to the worst grade.

For AESIs, summarization will be more extensive, reflecting the more detailed information collected. Information summarized will include number of events per subject, earliest onset day, duration (in days), causality, grade and seriousness of AESIs, outcome, actions taken with study drug, assorted physical characteristics of the AESIs, and demographic/baseline characteristics and PGA status of the subjects experiencing them. Each type of AESI will be summarized separately. If a subject has more than one treatment-emergent occurrence of an AESI, the subject's maximum duration, highest levels of causality and seriousness, maximum grade and generally the most extreme level of each characteristic will be summarized. If an AESI was ongoing at EOS, it will not be included in the duration summary.

A Kaplan-Meier figure will be generated for each AESI of time to first event. Subjects not experiencing the AESI will be censored at the date of study completion or discontinuation.

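### SAP 12.9.1 imputes a missing adverse event grade to the top of the scale with no cap, and the top of the protocol's printed scale is death

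*SAP*

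**What the plan says.** SAP 12.9.1 (Adverse Events) gives one rule for an event with no severity recorded: "Missing severity will be imputed to the highest severity level (most severe". It sets no ceiling and makes no exception for events that were not fatal.

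The severity scale comes from Protocol 8.2.1.1. The investigator makes an "assessment of the severity of each AE and SAE according to the National Cancer Institute Common Terminology Criteria for Adverse Events (CTCAE), v. 5.0". "For terms not specified with the CTCAE", Table 4 applies instead. Table 4 is the only list of grades printed in either document. It runs from 1 to 5: Grade 3 begins "Severe or medically significant but not immediately life-threatening", Grade 4 is life-threatening, and Grade 5 is "Death related to adverse event".

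The SAP reports severity as this grade. One planned table is "All TEAEs by SOC, PT, and maximum CTCAE grade". The subject-level rule is: "For summaries of TEAE CTCAE grade, a subject will be classified according to the worst grade". For events of special interest (contact dermatitis, folliculitis, headache), a subject with more than one occurrence is summarized by "maximum grade and generally the most extreme level of each characteristic will be summarized".

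Fatality is also captured without using the grade. Protocol 8.3.2 has Fatal as a separate outcome category, and the overall summary in SAP 12.9.1 has its own Death row.

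**The concern.** A worst-case rule for missing severity is a familiar conservative device on a mild, moderate, severe scale. On a scale whose last level is death, the same wording produces a value that the rest of the record can contradict. If an ungraded headache resolved, its outcome field says so, yet the grade table would place it in the row for fatal events.

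What is at stake is the credibility of the safety tables in a study that Protocol 1.1.2 describes as pivotal and intended to support registration. A Grade 5 entry that disagrees with the Death row has to be explained. No efficacy result is touched, and SAP 12.9 plans no formal comparison of safety data.

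**Working it through.** The plan states no figure on this point, so there is nothing to reproduce. The check is to apply the rule to the scale and follow the result through the planned tables.

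**Step 1. Value imputed.** The levels in Table 4 are 1, 2, 3, 4 and 5. The highest is max{1, 2, 3, 4, 5} = 5, defined as death. This is certain only for terms graded by Table 4. For CTCAE-listed terms the available grades are not printed in the documents, so using 1 to 5 there is an assumption.

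**Step 2. Where the value goes.**

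| Output | Source of the value | Effect of an imputed Grade 5 |
|---|---|---|
| TEAEs by SOC, PT and maximum grade (SAP 12.9.1) | CTCAE grade, worst per subject | Subject moves to Grade 5 |
| Special-interest grade summary (SAP 12.9.1) | Maximum grade per subject | Subject moves to Grade 5 |
| AE listing (SAP 12.9.1) | Grade and outcome both listed | Not said whether imputed grades are shown; the recorded outcome is unchanged |
| Death row, overall summary (SAP 12.9.1) | Not derived from grade | No change |
| Outcome field (Protocol 8.3.2) | Investigator's record | No change |

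**Step 3. Reach within a subject.** SAP 12.9.1 counts and classifies subjects at each level of summarization. Take a subject with an ungraded headache and a Grade 2 event under another SOC. The imputed value sets the headache row, the row for its SOC and any overall row to Grade 5. The rows for the other event remain at Grade 2.

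**Step 4. Size.** Planned arms are about 333 (tapinarof) and 167 (vehicle), from SAP Section 6. With k affected subjects in an arm, the false Grade 5 incidence is k/n.

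- k = 0: no effect.
- k = 1: 1/333 = 0.30%; 1/167 = 0.60%.
- k = 5: 5/333 = 1.50%; 5/167 = 2.99%.

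The documents do not give the number of missing grades. The range 0 to 5 is an assumption for illustration, and planned arm sizes stand in for the Safety population.

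**Step 5. Consistency inside the SAP.** Section 9 ends its missing-data rules by saying that safety endpoints, among others, are not imputed. Section 12.9.1 imputes severity and relatedness, and Section 9 itself imputes partial adverse event dates. The programmer has two statements that do not agree.

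**The case against.** The strongest reply is that the SAP never names Grade 5. The word severe belongs to Grade 3 on Table 4, and Grade 5 describes an outcome rather than an intensity, so the author may have meant Grade 3 or the highest non-fatal grade. That is possible, but the sentence says the highest level, and Grade 3 is third of five. Nothing in either document limits the rule to the lower reading, so the sentence needs correcting whichever was meant.

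Second, grades should seldom be missing. Protocol 8.2.1.1 requires severity on the case report form and in source, 8.2.2 requires full documentation of every event, and Section 9 provides for queries. This stands, and it is why the point is minor. But the rule operates only when those safeguards have failed.

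Third, the protocol also collects a mild, moderate, severe item for events of special interest (8.1.3), which has no death level. That is correct, and the rule does no harm there. The SAP nevertheless summarizes grade for those events as well.

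A reader might also infer more than the documents support:

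- **That the trial would report deaths that did not occur.** The Death row and the Fatal outcome are not derived from grade, so no death count changes.
- **That one ungraded event overrides all of a subject's grades.** It does so only at summary levels that include the event.
- **That the defect is proven for every term.** The 1 to 5 range is printed only for terms outside the CTCAE.
- **That Grade 3 is the evident replacement.** Nothing in the documents supports it, and it is less conservative than the SAP's stated intent.

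**Conclusion.** Wrong as written; minor severity. Followed literally, the rule classifies a non-fatal ungraded event as Grade 5 in the maximum-grade table and in the special-interest grade summary, against the trial's own outcome data. This is a stated rule that yields a false entry, not merely missing detail.

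The conclusion rests on a literal reading of the SAP sentence and on Table 4. For CTCAE-listed terms it also needs the assumption that the same range applies. The size is conditional: zero if every event is graded, and otherwise about 0.3 percentage points per affected tapinarof subject or 0.6 per affected vehicle subject at planned arm sizes.

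**What to change.** Replace the sentence in SAP 12.9.1 with a rule that does the following:

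1. Assigns Grade 5 only when the recorded outcome is Fatal.
2. For every other event with a missing grade, either imputes the highest non-fatal grade (Grade 4 on Table 4, which keeps the worst-case intent) or reports a separate missing-grade category. The SAP should choose one before unblinding.
3. Footnotes the number of imputed or missing grades, by arm, in each table affected.
4. Applies the same rule to the grade summaries for events of special interest.

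Then amend the closing statement of SAP Section 9 so that it excepts the adverse event rules in 12.9.1 and the date rules in Section 9, or withdraw the imputation in 12.9.1 so that the two agree.

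The cost is a sentence or two in the SAP and one programming condition on the outcome field. No additional data are needed, because outcome is already collected for each event.

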4.6.1. Reasons for Withdrawal from the Study

Study drug will be discontinued for any of the following reasons:

- Subject has an AE that is considered to be related to study drug or procedures AND is severe enough to warrant treatment discontinuation, as determined by the Investigator (Section 8.1).
- Subject requires concurrent prohibited medication during the study. If, in the opinion of the Investigator and the study Medical Monitor, such medication will not interfere with the conduct or interpretation of the study or compromise the safety of the subject, then the subject may continue to receive study drug. If the subject is discontinued from study drug, they may remain in the study for safety assessments as needed, at the discretion of the Investigator and Medical Monitor.
- Pregnancy
- Any Grade 3 or 4 AE considered causally related to study drug (Section 8.2.2)

Study drug may be discontinued for any of the following reasons:

- Subject noncompliance

- Investigator noncompliance
- Discontinuation of the study at the request of the Sponsor, regulatory agency, or an Institutional Review Board (IRB)/Independent Ethics Committee (IEC).

If a subject meets a withdrawal criterion during treatment, an Early Termination visit will be required (Section 7.5).

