10.4.3. Safety Analyses

The Safety Population will be used in the analysis of safety data. Data will be listed by subject and treatment and summarized by treatment. No formal statistical comparisons will be made for safety data.

The number and proportion of subjects with TEAEs will be summarized by treatment, system organ class, and preferred term for all TEAEs, all TEAEs considered by the Investigator to be related to study drug, all SAEs, and all TEAEs leading to study drug discontinuation. Summaries of AEs will be presented separately for double-blind and open-label treatment phases. All AE summaries will include information for AEs that occurred after administration of the first dose of study drug until completion of the final study visit. Data listings will be provided for subjects who discontinued the study due to an AE and for subjects with an SAE.

Selected laboratory data will be analyzed using descriptive summary statistics and will be presented by study visit and treatment group, including the number of non-missing observations, mean and SD, median, upper and lower quartiles, minimum and maximum for values and changes from Baseline. Categorical safety data will be analyzed using frequency tables and, if applicable, shift tables.

Vital signs will be listed by subject and summarized by visit.

Mean scores from the LTS will be summarized by visit.

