## 12. STATISTICAL EVALUATION

### 12.1 Subject Disposition

The number and percentage of subjects screened, screen failed along with reason for screen failures, randomized, included in each analysis population, completing 12-Week Double-Blind treatment, completing the study, withdrawing from treatment (together with the reasons for withdrawal), withdrawing from the study (together with the reasons for withdrawal), and subjects

excluded from PP population (together with the reasons for exclusion) will be summarized using frequencies and percentages by treatment group. For subjects who have completed the 12-Week treatment, the number and percentage of those who elect to enroll in the open-label study will be summarized.

Enrollment and disposition will be listed by subject. Screen failures and subjects not randomized will also be listed by subject.

The number of days in the study (date of study completion / discontinuation minus date of Day 1 plus 1) will be summarized descriptively by treatment group.

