## **13. CHANGES FROM THE PROTOCOL AND PLANNED ANALYSES**

The protocol specified change over time in physical component score and mental component score as measured by the SF-36 questionnaire as an exploratory endpoint. Scoring rules for the RAND 36-Item Health Survey (Version 1.0) are provided for the eight domain scores but not for the physical component score or the mental component score. Hence, summaries of the eight domain scores are planned.

No other changes from the protocol in planned analyses are noted. Any additional statistical analyses to handle modifications to study conduct and/or missing data due to the COVID-19 pandemic have been documented in Section 12.11 above in this SAP and will be finalized prior to database lock and unblinding of the study.

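### The SAP defines its discontinuation table by SOC and preferred term on leaving the study; the protocol defines it on stopping study drug

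*SAP*

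**What the plan says.** Protocol 10.4.3 (Safety Analyses) sets the level of tabulation: numbers and proportions are to be "summarized by treatment, system organ class, and preferred term for all TEAEs", and then for further categories that end with "all SAEs, and all TEAEs leading to study drug discontinuation". The synopsis says the same. For discontinuation, the protocol's table therefore concerns events that stopped the drug.

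SAP 12.9.1 (Adverse Events) uses two different definitions:

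- The overall incidence summary has a line for "Any TEAE leading to study drug discontinuation" and another for serious TEAEs with the same consequence. Neither is broken down by term.
- The SOC/PT summary is planned for all TEAEs and "also for treatment-related TEAEs, TEAEs leading to study discontinuation and serious TEAEs". Here the criterion is leaving the study.

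The same section plans separate listings: "Serious AEs (SAEs), TEAEs leading to study discontinuation, TEAEs related to study drug will also be listed separately". SAP 13, after describing the change to the SF-36 scoring, states: "No other changes from the protocol in planned analyses are noted".

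**The concern.** The two criteria select different sets of events whenever a subject can stop the cream without leaving the trial. If the SAP is programmed as written, no planned output shows, by arm and preferred term, which events stopped dosing, although the protocol promised that summary. A reader of the study report would see an overall count of subjects who stopped drug for a TEAE, next to a term-level table built on another criterion. If the sets differ, the two could not be reconciled.

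This is a tolerability output in a pivotal study intended to support registration. What is at stake is completeness against the protocol and a readable account of tolerability. No hypothesis test depends on it, since SAP 12.9 makes no formal safety comparisons.

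**Working it through.** There is no stated figure to reproduce. The check compares the passages.

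**Step 1: which set each output uses.** Let D be the TEAEs that led to stopping study drug, and S the TEAEs that led to leaving the study.

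| Output | Protocol 10.4.3 | SAP 12.9.1 |
|---|---|---|
| Overall incidence line | not itemised | D |
| SOC/PT discontinuation table, by arm | D | S |
| Separate listing | subjects who left the study because of an AE (S) | S |

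Only the middle row disagrees. The listing row agrees.

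**Step 2: can D and S differ under these documents?**

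- Protocol 4.6 lets a subject stop treatment, withdraw from participation, or both. Protocol 4.6.2 has the primary reason recorded on the same and/or basis.
- SAP 12.1 tabulates the two outcomes separately, each with reasons: "withdrawing from treatment (together with the reasons for withdrawal), withdrawing from the study (together with the reasons for withdrawal".
- Protocol 8.1.3 says that for contact dermatitis, folliculitis and headache, the three adverse events of special interest (AESIs), drug may be stopped at the investigator's judgment and restarted once the event resolves. A restart requires the subject to be still in the study.
- Protocol 4.6.1 says of subjects taken off drug that "they may remain in the study for safety assessments as needed". This sentence belongs to the prohibited-medication criterion, not to the adverse event criteria. It shows that being off drug but on study is a recognised state; it does not show that it follows an adverse event.

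So D and S are separable by design, and an event can belong to D without belonging to S.

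**Step 3: what happens to an event in D but not in S.** Under the SAP it is:

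- counted in the overall line for drug discontinuation;
- counted under its preferred term in the all-TEAE SOC/PT table and in the tables by maximum grade and by causality;
- shown in the full AE listing, which carries the action taken with study drug;
- for an AESI, also covered by the summary of actions taken with study drug;
- absent from the SOC/PT discontinuation table.

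The loss is the one cross-classification of preferred term by whether the event stopped dosing, by arm, for terms other than the AESIs.

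**Step 4: how many events.** The number lost is the count in D but not in S, which lies between zero and all of D. The documents give neither the rate of stopping drug for a TEAE nor the share of those subjects who stay. The 25% loss to follow-up assumed in the sample-size section is neither of these rates and cannot stand in for them. No estimate is possible.

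**The case against.** The strongest case against is that D and S may nearly coincide for adverse events. Protocol 4.6.1 puts the drug-stopping criteria under a heading about withdrawal from the study, and meeting one during treatment requires an Early Termination visit. Protocol 7.5 describes that visit as being for subjects who withdraw early. Subjects permanently off drug for Grade 3 or 4 events are followed weekly, but are also encouraged to complete the withdrawal evaluations. All of this stands, and it is why the effect may be small or zero. It does not make the two terms equivalent, because Protocol 4.6, 4.6.2 and 8.1.3 and SAP 12.1 keep them apart.

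It can also be said that the SAP does not cancel the protocol's table. SAP 1 says it will not repeat every protocol definition, and its revision history describes the study-discontinuation summary as an addition. That argues against a deliberate replacement. Even so, 12.9.1 enumerates the SOC/PT tables and the protocol's table is not among them. If it is still intended, it should be listed; if not, SAP 13 should say so.

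Three stronger readings are tempting, and the documents do not support them:

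- A reader might infer that drug-stopping events vanish from term-level reporting. They do not; step 3 shows where they appear.
- A reader might infer that the SAP's study-discontinuation listing is also a departure. Protocol 10.4.3 asks for listings of subjects who left the study because of an AE, so the listing conforms.
- A reader might want a count of lost events, or suppose that study exits caused by an AE will be coded to other reasons. Any count would rest on invented rates, and Protocol 8.2.2 requires withdrawal from the study because of an AE to be recorded as such.

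**Conclusion.** The point holds for one table. SAP 12.9.1, followed as written, does not produce the SOC/PT summary of TEAEs leading to study drug discontinuation that Protocol 10.4.3 and the synopsis require, and SAP 13 does not declare the difference. The section is also inconsistent within itself, using one criterion for the overall line and the other for the term-level table.

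The textual mismatch rests on no assumption. Its practical size depends on how many subjects stop drug for a TEAE and stay in the study, which the documents do not say. If every such subject also leaves because of that event, the two tables are identical and nothing is lost. The change is worth making because the protocol specifies the table and the field needed to build it is already planned for the AE listing.

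**What to change.** In SAP 12.9.1, add a table by treatment, SOC and PT of TEAEs leading to study drug discontinuation, selected on the action taken with study drug. State which recorded values of that field qualify, because Protocol 8.1.3 uses the language of discontinuation for a stop that may be followed by a restart. Use the same selection for the overall incidence lines, so that the table and the lines reconcile.

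Keep the study-discontinuation SOC/PT table as an additional output, and leave the study-discontinuation listing as it is. If the sponsor does not want the protocol's table, the alternative is to declare and justify its omission in SAP 13.

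The cost is a short change of wording and one extra descriptive table. No new data collection is needed.
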